6.7.2.2 Expansion Part (GEN3017 Monotherapy)

Dose modification guidance used in the dose escalation part (see Section 6.7.2.1) will be applied to expansion GEN3017 monotherapy cohorts as appropriate and will be modified based on emerging data.

6.7.2.3 Dose Delays of GEN3017 Due to COVID-19 Infection

During the trial, GEN3017 should be withheld in subjects with a suspected COVID-19 infection or with a positive viral test. GEN3017 may be resumed if the following criteria are met:

Symptomatic subjects:

Confidential Page 79 of 162

a. This may exclude any asymptomatic isolated laboratory abnormalities without any clinical consequences such as hypoalbuminemia, hypophosphatemia, hyponatremia, etc.

b. If recurrent grade 3/4 hematological toxicities are not manageable and no treatment effect from GEN3017 has been observed after Day 42, GEN3017 may be discontinued at the investigator's discretion. In subjects benefiting from GEN3017 treatment, there is no limit to the number of hematological toxicities as long as they can be managed.

Document Number: TMF-380962

Version: 3.0

Subject has recovered, defined as resolution of fever without use of antipyretics and improvement in respiratory symptoms (eg, cough, shortness of breath), AND subject has obtained 2 negative molecular (eg, PCR) tests or negative antigen tests with results ≥ 24 hours apart, and it has been 7-10 days after the 2nd negative test.

Genmab

• Asymptomatic subjects:

 Subject has obtained 2 negative molecular (eg, polymerase chain reaction [PCR]) tests or negative antigen tests with results ≥ 24 hours apart and it has been 7-10 days after the 2nd negative test.

6.7.2.4 Tumor Flare or Pseudoprogression

Pseudoprogression, a phenomenon with an influx of immune responsive cells into a lesion that causes clinical and imaging findings during treatment suggestive of progressive disease despite evidence of clinical benefit, has been reported in lymphomas treated with immunotherapies such as rituximab (Han et al., 2009; Skoura et al., 2016), immunomodulatory drugs (eg, lenalidomide (Witzig et al., 2011)), anti-PD-1 inhibitors (Ansell et al., 2015; Lesokhin et al., 2016; Westin et al., 2014), and bispecific antibodies (eg, glofitamab (Dickinson et al., 2022)). It is important to differentiate pseudoprogression from true tumor progression to avoid the premature discontinuation of GEN3017.

6.7.2.4.1 Criteria for Continuing GEN3017 Treatment During Suspected Pseudoprogression

During the trial, when the investigator believes that a subject is deriving clinical benefit from GEN3017 treatment despite radiographic evidence of progressive disease, investigators are encouraged to continue GEN3017 treatment until the next scheduled imaging assessment, provided the following criteria are met:

- There is an absence of symptoms and signs (including worsening of laboratory values) indicating progression of disease.
- There is no decline in ECOG performance status (Section 10.5).
- There is an absence of tumor progression at critical anatomical sites including the central airway, the great vessels, and other organs or tissues where compromised function secondary to tumor progression would be expected to result acutely in severe and/or irreversible disability or death.

Subjects continuing GEN3017 therapy, despite apparent radiographic progression, will be encouraged to undergo a repeat tumor biopsy to assess whether increases in tumor volume are due to immune cell infiltration or neoplastic proliferation, provided that such a biopsy can be performed safely on a non-target lesion.

In subjects categorized as having suspected pseudoprogression, it is mandatory to obtain a repeat imaging in the next scheduled imaging assessment (Section 1.3) or earlier if clinically indicated.

Confidential Page 80 of 162

Version: 3.0

6.7.2.4.2 Retreatment After Discontinuing From GEN3017 Treatment Due To Suspected Pseudoprogression

Subjects discontinued from GEN3017 treatment due to suspected pseudoprogression, who later achieve PR or CR without receiving any other anticancer therapy after the last dose of GEN3017, will be allowed to enter the "post-treatment follow-up" period for efficacy. These subjects may be eligible for retreatment if, after discussion with the sponsor's MM, the MM agrees to retreat the subject and the subject meets eligibility criteria.

Genmab

6.7.2.5 Monitoring of Rapid Tumor Progression

Rapid tumor progression (ie, an acceleration of disease activity with disease progression according to the 2014 Lugano classification prior to completion of 3 cycles of GEN3017 treatment) will be closely monitored. If a subject experiences rapid tumor progression per the investigator's assessment, the investigator should promptly discuss this with the sponsor's MM and the subject should be discontinued from GEN3017 treatment.

During the conduct of the trial, and after at least 3 subjects have been treated with GEN3017 and received at least one dose of GEN3017, if >33% of subjects (regardless of the DL or if during phase 1 or phase 2a) experience rapid progression, trial accrual will be halted and a full review of these events will be performed by the DEC and Safety Committee for phase 1 and Safety Committee for phase 2a, respectively. Patient accrual will not resume until approved by the DEC and Safety Committee (phase 1) or Safety Committee (phase 2a).

6.7.3 Safety Stopping Guidance for the Trial

The trial can/will be stopped for unacceptable toxicity as per recommendations from DEC and Safety Committee in dose escalation or Safety Committee in expansion and based on a risk-benefit assessment. Fatal events considered related to GEN3017 should always be assessed by the DEC and Safety Committee in dose escalation or Safety Committee in expansion.

In order to ensure subject safety during dose escalation, if any of the boundaries in Table 6-5 are crossed for a DL in 1 of the indications (considered independently), a prompt comprehensive review of the safety data will be conducted to determine if the trial should be stopped. In particular, for treatment-related grade 5 AEs, if the boundary is crossed the enrollment into any dose escalation DL is paused and a subsequent review will occur.

Table 6-5 Safety Stopping Guidance in Study GCT3017-01	Table 6-5	Safety Stopping Guidance in Study GCT3017-01
--	-----------	--

Number Dosed at DL	1	2	3	4	5	6	9	12
Grade 3 or greater CRS/ICANS ^a	-	-	3	≥3	≥3	-	≥5	≥5
Grade 4 or greater CRS/ICANS	-	2	≥2	≥2	≥2	≥2	≥3	≥3
Treatment-related grade 5 AEs	1	≥1	≥1	≥1	-	≥2	≥2	≥2

AE=adverse event; CRS=cytokine release syndrome; DL=dose level; ICANS=immune effector cell-associated neurotoxicity syndrome.

The boundaries assume acceptable incidences of:

• 15% incidence for grade 3 or greater CRS/ICANS

Confidential Page 81 of 162

a. Which has not resolved to \leq grade 2 within 48 hours following adequate intervention.

Document Number: TMF-380962

Version: 3.0

• 5% incidence for grade 4 or greater CRS/ICANS

• 1% incidence for treatment-related grade 5 AEs

When given an acceptable incidence, the probability for crossing the boundary at any monitoring time is approximately 5%.

Genmab

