4 TRIAL DESIGN

4.1 Description of Trial Design

This is a phase 1/2a, open-label, multicenter, trial to evaluate the safety, tolerability, pharmacokinetics, pharmacodynamics, and preliminary efficacy of GEN3017 in subjects with R/R CD30+ cHL or R/R CD30+ TCL.

Genmab

The trial will be conducted in 2 parts: dose escalation (phase 1; Section 4.1.1) and expansion (phase 2a; Section 4.1.2). A diagram of the trial design is provided in Section 1.2.

Each part will consist of the following:

- 1. Screening period (up to 21 days prior to Cycle 1 Day 1),
- 2. Treatment period (Cycle 1 Day 1 until GEN3017 treatment discontinuation),
- 3. Follow-up period (ie, 60-day safety follow-up from the last dose of GEN3017 or before the initiation of a new anticancer treatment, whichever comes first; post-treatment follow-up for subjects who discontinue GEN3017 prior to disease progression; and survival follow-up by telephone contact or retrospective chart review until death, lost to follow-up, or the End of Trial, whichever comes first).

The MTD of each disease cohort, if reached, along with the maximum administered dose (MAD) and RP2D of each disease cohort will be determined based on the totality of the data of each disease cohort.

Approximately 120 subjects (60 in each disease cohort) are expected to be enrolled in the dose escalation part of the trial and approximately 120 subjects are expected to be enrolled in the expansion part of the trial.

In phase 1 (dose escalation), subjects who are not DLT-evaluable will be replaced (see Section 4.1.1.5). In phase 2a (expansion), subjects who discontinue from the trial will not be replaced.

During dose escalation, a DEC will review the preliminary data from subjects treated at a specific dose level (DL) according to DEC Charter and evaluate potential DLTs. The DEC will make recommendations on escalating to the next DL and/or propose the RP2D/MTD/MAD to the Safety Committee, who will have to endorse the proposed DL before subjects at the next DL can be enrolled, as well as the dose(s) selected for expansion.

During expansion, the Safety Committee will assess the totality of safety information of the trial and identify additional safety signals. Refer to the Committees Structure in Section 10.1.8 for details.

Confidential Page 45 of 162

Document Number: TMF-380962

Version: 3.0

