4.1.1 Dose Escalation

In dose escalation, GEN3017 will be tested in 2 disease cohorts:

 R/R CD30+ cHL Cohort (see Sections 5.1 and 5.2 for inclusion and exclusion criteria): Adult subjects 18 years and older will be enrolled. In the US and Australia, subjects 16 to 17 years old will be eligible to participate in the R/R CD30+ cHL dose escalation cohort (Section 10.18.3 and 10.18.4, respectively).

Genmab

and

R/R CD30+ TCL Cohort (see Sections 5.1 and 5.2 for inclusion and exclusion criteria):
 Adult subjects 18 years and older will be enrolled.

Dose escalations for each disease cohort will be conducted independently. The modified Bayesian optimal interval design (mBOIN) design will be applied to guide dose escalations for each disease cohort separately. The MAD, RP2D, and MTD (if reached) for the 2 disease cohorts will be determined based on the observed toxicity with each. Population PK modeling may be explored to facilitate selection of the optimal dosing and dosing schedule.

Dose escalation will start with an accelerated titration with single-subject DLs followed by standard titration of 3-subject DLs. For each disease cohort, up to 3 DLs will enroll 1 subject for the accelerated titration part. The trigger point to expand a 1-subject DL into a 3-subject DL (eg, adding 2 more subjects to a single-subject DL) is the observation of any of the following events during the DLT evaluation period:

- Any hematologic toxicity ≥ grade 2 (according to Common Terminology Criteria for Adverse Events (CTCAE)
- Any non-hematologic toxicity ≥ grade 2 (per CTCAE)
 - o Any CRS ≥ grade 2 (per ASTCT criteria (Lee et al., 2019))
 - o Any ICANS ≥ grade 2 (per ASTCT criteria (Lee et al., 2019))
- A DLT (see Section 6.7.1)
- Or a DL CCI is being explored.

Adverse events (AEs) of specified grades mentioned above, regardless of relationship to GEN3017, should be considered relevant for transitioning from single subject into the standard 3 subjects at the initial single-subject DLs, unless the event can clearly be determined to be unrelated to the drug.

Confidential Page 46 of 162

Version: 3.0

This marks the start of the standard titration part, where the DL sizes by default are 3 subjects each. For the standard titration part, Table 4-2 provides guidance to the DEC for the next DL.

- For an investigated, non-cleared DL, there should be at least 2 nights between administration of the first dose to the first subject and the second subject within the same DL.

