- Any additional subjects enrolled in the investigated, non-cleared DL should receive the first dose at least 1 day apart.
- For a DL cleared for safety as recommended by the DEC and Safety Committee, there is no
 specific time frame for receiving the first dose among subjects (ie, additional subjects may be
 treated in parallel at the respective DL that are considered safe (Section 4.1.1.6).

GEN3017 will be tested at DLs ranging from CC in CC cycles. Intrapatient dose escalation will not be allowed. At each DL, DLTs will be assessed in the first treatment cycle all subjects are required to be hospitalized for 24 hours after GEN3017 administration (Section 6.1). Additional and prolonged hospitalization for monitoring subject's safety during GEN3017 administration at investigator's discretion.

Additional dose levels below the currently deemed safe dose level may also be explored for further substantiation of safety, PK, and PD based upon emerging data.

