6.7 Dose Modification and Stopping Rules

6.7.1 Dose-Limiting Toxicity (Dose Escalation of GEN3017)

Treatment delays during the first CCI of the start of the DLT window are allowed if they are less than 1 cycle in length; under these circumstances, the DLT window can be extended up to CCI.

All DLTs are required to be reported to the sponsor within 24 hours of occurrence.

Confidential Page 74 of 162

Document Number: TMF-380962

Version: 3.0

All AEs including DLTs will be graded for severity according to the National Cancer Institute (NCI)-CTCAE, v5.0 unless otherwise specified. CRS and ICANS will be evaluated according to the ASTCT criteria (Lee et al., 2019). Clinical tumor lysis syndrome (CTLS) will be evaluated according to the Cairo-Bishop classification ((Coiffier et al., 2008); Section 10.15).

Genmab

The occurrence of any of the toxicities outlined in this section will be considered as a DLT except those that are clearly due to the underlying disease or extraneous cause:

- All grade 5 toxicities
- Hematological toxicities listed below:
 - o Grade 4 neutropenia (ie, absolute neutrophil count $<0.5\times10^9$ cells/L [$<500/\mu$ L]) lasting >7 days not attributable to underlying disease
 - o Grade 3 and grade 4 febrile neutropenia (neutrophil count <1.0×10⁹ cells/L with a single temperature of >38.3 °C [100.9 °F] or with a sustained temperature of ≥38 °C [≥100.4 °F] for more than 1 hour) lasting >2 days
 - Grade 4 thrombocytopenia (platelet count ≤25.0×10⁹ platelets/L [<25,000/μL]) for >7 consecutive days not attributable to underlying disease, or ≥ grade 3 thrombocytopenia (<50.0×10⁹ platelets/L) of any duration with clinically significant bleeding or ≥ grade 3 thrombocytopenia requiring a platelet transfusion
 - Grade 4 anemia
- Non-hematological toxicities listed below:
 - o Grade 4 CRS according to ASTCT criteria (Lee et al., 2019)
 - o Grade 3 CRS according to ASTCT criteria (Lee et al., 2019) which has not resolved to ≤ grade 2 within 48 hours following adequate intervention
 - o Grade 4 ICANS according to ASTCT criteria (Lee et al., 2019)
 - o Grade 3 ICANS according to ASTCT criteria (Lee et al., 2019) which has not resolved to ≤ grade 2 within 48 hours following adequate intervention
 - o TLS grade 3 that has not resolved within 5 days
 - o TLS grade 4
 - Any ≥ grade 3 (severe or life-threatening) non-hematological toxicities, excluding the following:

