 - Laboratory values out of normal range that do not have any clinical consequence, are clinically transient in nature, and that resolve within 7 days (including electrolyte abnormalities that respond to medical intervention)
 - Grade 3 aspartate transaminase and/or grade 3 alanine transaminase returning to grade 1 or baseline in ≤10 days

Confidential Page 75 of 162

Document Number: TMF-380962

Version: 3.0

• Grade 3 nausea that responds to optimal antiemetic treatment in <3 days

- Grade 3 vomiting that responds to optimal antiemetic treatment in ≤ 3 days
- Grade 3 diarrhea that responds to optimal antidiarrheal treatment in \leq 3 days
- Grade 3 fatigue/asthenia when fatigue/asthenia was present at baseline or that lasts for <14 days after the last dose of GEN3017

Genmab

• Grade 3 amylase or lipase that is not associated with symptoms, or clinical manifestations, or radiological imaging of pancreatitis

Note: AEs of specified grades, regardless of relationship to GEN3017, should be considered relevant for dose escalation decisions, unless the event can clearly be determined to be unrelated to the drug. All of the AEs of specified grades should be classified as DLTs except those that are clearly and incontrovertibly due to the underlying disease or extraneous causes.

Frequent laboratory monitoring of complete blood count, including differential, should be initiated to document start and resolution of hematological AEs. All GEN3017-related AEs will be monitored and included in the evaluation of the toxicity profile of GEN3017 unless the event is clearly determined to be unrelated to GEN3017. AEs clearly not related to GEN3017 such as disease progression, environmental factors, unrelated trauma, etc, should not be considered as a toxicity event.

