10.2.3.2 Relationship to the Investigational Medicinal Product

The investigator must assess whether or not the event is related to the trial drug(s). The relationship is to be judged using the following terms:

• Related

Confidential Page 119 of 162

Document Number: TMF-380962

Version: 3.0

Not related

If the relationship changes over time, the last judgment by the investigator should be reported. Relatedness has to be assessed and reported from the first time the event is being reported.

A suspected adverse reaction is one in which there is a reasonable possibility that the trial drug(s) caused the AE, this means there is evidence to suggest a causal relationship between the trial drug(s) and the AE (ie, considered related). Refer to the GEN3017 IB.

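### In dose escalation, a death that counts as a DLT but is coded not related triggers neither the 6.7.3 pause nor the 6.7.3 fatal-event assessment, and no visible text requires review before the next first dose at that level

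*Combined protocol and SAP*

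**What the plan says.** **Which deaths are DLTs.** Section 6.7.1 lists every grade 5 toxicity. Its note makes graded events relevant to escalation whatever their relationship to the drug, unless they are clearly unrelated, and says that they "should be classified as DLTs except those that are clearly and incontrovertibly due to the underlying disease or extraneous causes". On reporting: "All DLTs are required to be reported to the sponsor within 24 hours of occurrence".

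**Which deaths are related.** Section 10.2.3.2 is a separate two-way coding by the investigator. An event is a suspected reaction when "there is a reasonable possibility that the trial drug(s) caused the AE", which the section explains as evidence pointing to a causal link.

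**What 6.7.3 attaches to a death.** In dose escalation, "Fatal events considered related to GEN3017 should always be assessed by the DEC and Safety Committee". The fatal row of Table 6-5, and the pause on enrollment into every escalation level, cover treatment-related grade 5 events only. The section does not say whose attribution counts.

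**What governs the next first dose.** Under section 4.1 the DEC evaluates potential DLTs and makes its recommendation to the Safety Committee, "who will have to endorse the proposed DL before subjects at the next DL can be enrolled". Inside a level not yet cleared, section 4.1.1 sets time gaps: "at least 2 nights between administration of the first dose to the first subject and the second subject", and then "Any additional subjects enrolled in the investigated, non-cleared DL should receive the first dose at least 1 day apart". For the accelerated part it defines "The trigger point to expand a 1-subject DL into a 3-subject DL (eg, adding 2 more subjects to a single-subject DL") by a list of events that includes any DLT. Section 4.1.1.5 says that such levels can be expanded, and allows 2 subjects of over-recruitment.

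**The concern.** The protocol applies two standards to the same death. The DLT standard asks whether another cause is clear; the 6.7.3 standard asks whether the drug is considered responsible. A death with no positive evidence against the drug and no clear alternative cause falls between them. It is a DLT, yet 6.7.3 attaches nothing to it.

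The timing rules do not obviously close the space. The committee endorsement in 4.1 is written for the next dose level, not for the next subject at the same level. The staggers count from first doses, not from events. At a single-subject level the DLT opens 2 more places at the same dose, with no exception for grade 5. At stake is whether subjects in a first-in-human trial can receive a first dose at a level where drug causation of a death has not been excluded, with only sponsor discretion to hold them back.

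**Working it through.** **1. The plan's own figure.** Table 6-5 claims about a 5% chance of crossing a boundary at the acceptable incidence. For the fatal row (1 event at n = 1 to 4, no look at 5, 2 events at 6, 9 and 12; true rate 1%), the cumulative crossing probability is 1 − 0.99⁴ = 3.94% by n = 4, then 3.95%, 4.03% and 4.20% at n = 6, 9 and 12. It is 5.09% if the one-event boundary also applies at n = 5. The row reproduces for what it counts. A death coded not related adds nothing to that count at any n.

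**2. The standards side by side** (death in the DLT window, level with 1 to 4 dosed):

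| Coding of the death | DLT (6.7.1) | Assessment (6.7.3) | Pause (6.7.3) |
|---|---|---|---|
| Related | yes | yes | yes |
| Not related, other cause clear | no | no | no |
| Not related, other cause not clear | yes | no | no |

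The CRS/ICANS rows of Table 6-5 carry no relatedness condition, but need at least 2 events (grade 4 or greater) or 3 (grade 3 or greater), and lead to a review rather than the stated pause.

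**3. What stands between that death and the next first dose.**
- Required: report to the sponsor within 24 hours (6.7.1); prompt notice to the medical monitor and a full assessment of the event and the subject's benefit-risk (6.7.2.1); DEC evaluation, with meetings tied to completion of DLT periods (4.1, 10.1.8); sponsor control of slots (6.4.1) and confirmation of eligibility before enrollment (section 5).
- Discretionary: ad hoc investigator meetings (4.1.1.7); a Safety Committee hold (10.1.8).
- Required review before the next first dose at that level: none found.

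**4. Exposure.** At a single-subject level, 3 − 1 = 2 further subjects, or 5 − 1 = 4 with over-recruitment. While a 3-subject level fills at the fastest permitted stagger, first doses fall on days 0, 2 and 3 (then 4 and 5). A death in the first subject known by day 1 leaves 2 undosed (4 if over-recruited); known on day 2, 1 (3); from day 3, none (from day 5 if over-recruited). Slower filling widens the window.

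**5. Risk to those exposed.** P(at least one DLT in k) = 1 − (1 − p)ᵏ, with p the range over the four Appendix 17 scenarios. Single-subject levels are at most the first three (4.1.1.5).

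| Level | p | k = 2 | k = 4 |
|---|---|---|---|
| DL1 | 0–1% | 0–2% | 0–4% |
| DL2 | 1–2% | 2–4% | 4–8% |
| DL3 | 1–10% | 2–19% | 4–34% |

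**6. Frequency.** The documents give no rate q for such deaths, so q is assumed.
- At least one in the 6 single-subject slots (3 levels × 2 cohorts), 1 − (1 − q)⁶: 3.0%, 5.9% and 11.4% for q = 0.5%, 1% and 2%.
- Expected number over 120 escalation subjects, 120q: 0.6, 1.2 and 2.4.
- Expected number on Appendix 17 totals (2 × 23.4 to 2 × 32.9 = 46.8 to 65.8 subjects, backfill excluded): 0.23–0.33, 0.47–0.66 and 0.94–1.32.
- These are expected counts, not ceilings. At q = 1% and 120 subjects, P(two or more) = 1 − 0.99¹²⁰ − 1.2 × 0.99¹¹⁹ ≈ 34%.

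**The case against.** The best defense has three parts. First, the class of event is thin. A reasonable possibility of causation is a low bar, so a first-in-human death with no clear alternative would often be coded related and engage 6.7.3 in full. Fatal CRS and ICANS, the main identified risks, are defined in the grading appendices as deaths principally due to those syndromes. Second, the sponsor is not passive: it knows within a day, controls slots, confirms eligibility and can stop enrollment through the Safety Committee. Third, a subject with a DLT already counts as evaluable under section 9.2, so at a one-subject level the DLT evaluation is arguably complete at death and a DEC meeting is due. Nothing says that the added 2 subjects bypass it.

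The first part stands and makes the event rare. The second stands as far as it goes: a means to hold is not a requirement to hold, and a subject whose eligibility was confirmed before the death has already passed that check. The third is a fair reading of the meeting schedule, but the schedule does not say that the meeting precedes the next first dose. The DEC Charter, or the redacted parts of 4.1.1 and 6.7.1, might say so.

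A reader might go further and infer that such a death escapes review altogether, or that later remain and escalate decisions are taken without the DEC. The text does not support either. Section 4.1 has the DEC evaluate potential DLTs, and Table 4-2 guides the DEC after the DLT period. The gap is in timing.

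**Conclusion.** The point holds as a low-frequency safety gap. Followed as written, the visible rules permit 2 further first doses (up to 4) at a level where a death has counted as a DLT, before any required review.

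A reader might infer a much larger hazard by taking DLT probabilities of 10%, 20% or 30%, which give 19%, 36% or 51% for 2 subjects. The documents do not support those values at single-subject levels: in Appendix 17, 10% is reached only at DL3 and in two of four scenarios, 20% no earlier than DL5, and 30% no earlier than DL7. The death may itself signal more toxicity than the scenarios assume, and the risk would then be higher, but nothing in the documents sizes that. The harm is avoided only where review would close the level.

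The conclusion rests on three things: relatedness in 6.7.3 following the only coding rule given, which is the investigator's; the unseen Charter and redacted text not already requiring the review; and an assumed rate for such deaths.

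**What to change.** In 4.1.1 add: *After any grade 5 DLT, no further subject in that disease cohort receives a first dose at that DL or any higher DL until the DEC and Safety Committee have assessed the event.* Higher levels need to be included because a DLT death in a backfilled subject at a cleared lower level (4.1.1.6) would otherwise leave dosing above it open.

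In 6.7.3 widen the dose-escalation assessment to cover *fatal events considered related to GEN3017 and any grade 5 DLT*. Leave Tables 4-2 and 6-5 and the expansion text as they are.

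This takes two short edits in an amendment and uses the existing committees. Section 6.7.2.5 already has a hold-until-approved rule, though it is triggered by a rate of rapid progression above 33% rather than by a single event. The downside is an occasional short hold, within one disease cohort, for a death later judged unrelated: about 0.5 to 1.2 expected over escalation at the assumed 1% rate, with a real chance of more than one. If the Charter already requires this review, the edits only bring the protocol into line with it.
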